## 3.2 Dose and Dosing Regimen

Subjects will be randomized 1:1 into 1 of 2 weekly treatment sequences:

**Sequence A:** 0.5 g/kg IgPro20 for 24 weeks (Study Period 1) followed by 0.5 g/kg IgPro20 for 28 weeks (Study Period 2)

OR

**Sequence B:** placebo for 24 weeks (Study Period 1) followed by 0.5 g/kg IgPro20 for 28 weeks (Study Period 2)

In Study Period 3, subjects who show benefit (TIS  $\geq$  20 points) at Week 49 will receive open-label 0.5 g/kg IgPro20 until the end of the study ([Section 3.7](#)).

## 3.3 Scientific Rationale

### 3.3.1 Study Design Rationale

In this study, the EULAR/ACR classification criteria will be used to confirm the DM diagnosis. In short, the EULAR/ACR classification criteria assigns a numeric score to subjects with various clinical features such as skin and other clinical manifestations, muscle weakness patterns, laboratory evaluations, and muscle biopsy features. The aggregate score obtained will allow the subject to be classified with probable or definite IIM, and then presence of specific rash or other objective evidence (eg, muscle biopsy) will be used to identify the subjects with DM [[Lundberg et al, 2017](#)].

Evidence for the efficacy of immunoglobulin (IVIG or SCIG) treatment in patients with DM is limited. IVIG was shown to be efficacious in 2 randomized controlled studies of DM. The first study reported in 1993 by [Dalakas et al](#), randomized 15 subjects with refractory disease to either corticosteroids and placebo or corticosteroids and high dose IVIG (1 gram/kg/day  $\times$  2 days monthly for 3 months). The authors reported that subjects treated with IVIG had a significant improvement in scores of muscle strength ( $p < 0.018$ ) and neuromuscular symptoms ( $p < 0.035$ ) compared to subjects treated with placebo who had no change. The second study reported in 2008 by [Tian et al](#), randomized 60 elderly ( $> 60$  years of age) subjects with DM to either corticosteroids or corticosteroids and low dose IVIG (0.4 gram/kg/day  $\times$  3 days monthly for 3 months). The authors reported greater clinical and biochemical improvements in the group treated with IVIG compared to those who were not treated with IVIG and minor side effects. In addition to these 2 existing randomized controlled studies of IVIG therapy in DM, several prospective and retrospective open-label

studies have been conducted and are summarized in a systematic review [Wang et al, 2012]. Clinical improvement was reported in up to 93% of subjects in early and therapy-refractory DM/PM; the typical dose was 2 g/kg IVIG given over 3 to 6 months. It has been reported that long-term use of IgG therapy is safe and effective, but this has not yet been confirmed in clinical studies. In a retrospective long-term study, 42 subjects with DM were followed; 24 received IVIG therapy regularly. After 6 months of treatment, most IVIG-treated subjects (91.7%) presented with muscular disease remission, compared to 55.6% of non-IVIG-treated subjects ( $p = 0.007$ ). During long-term IVIG treatment (up to 48 months), 16.7% of subjects presented with muscular relapses, which is significantly less than those who received no or only a few IVIG courses. The overall relapse-free period from any DM symptom was  $38.5 \pm 24.3$  months [Kampylafka, 2012].

SCIG has also been shown to be efficacious in treating subjects with DM/PM in smaller uncontrolled studies [Schleinitz et al, 2008; Danieli et al, 2011; Danieli et al, 2014; Gelardi et al, 2014; Cherin et al, 2016]. Long-term use of SCIG therapy has been described by Cherin [Cherin et al, 2016]. In doses of 1.9 g/kg monthly, 19 subjects were treated for a mean of 18.8 months. Median doses infused were 180 mL/week using 2 infusion pumps; similar to the infusion parameters in this study. Although these smaller studies have shown promising results, no large-scale or randomized controlled studies are available to corroborate the efficacy of SCIG against placebo in subjects with DM, which is a reason for the initiation of this study.

This study will build on previous evidence that has shown efficacy in the first 3 to 6 months of IgG treatment and will investigate whether the initial improvement can be sustained for 6 months to up to 7 years.

The primary endpoint of this study is based on the TIS [Aggarwal et al, 2017]. The TIS is a sum response criterion which incorporates 6 weighted International Myositis Assessment and Clinical Studies (IMACS) CSMs, previously validated for the assessment of DM and PM [Rider et al, 2003; Rider et al, 2002]. They include physician and patient global activity on a 10-cm VAS, muscle strength measured by manual muscle testing (MMT-8), physical function measured by the Health Assessment Questionnaire, extramuscular global activity measured by the physician on a 10-cm VAS, and the most abnormal serum muscle enzyme. The TIS was evaluated on patient profiles using expert consensus (gold standard) and was validated using data from a clinical study [Oddis et al, 2013], the largest study done in DM and PM so far. A total improvement score (range: 0 to 100), determined by summing scores for each CSM, was based on improvement in and relative weight of each CSM. Thresholds for minimal, moderate, and major improvement were  $\geq 20$ ,  $\geq 40$ , and  $\geq 60$  points on the TIS.

The TIS was chosen as the basis for the primary endpoint of this study given the fact that no single CSM adequately covers all the domains in DM. For example, muscle enzyme levels can be normal in active DM, and active muscle weakness in DM can occur without active rash. The previously developed IMACS response criteria were based on at least 20% improvement in 3 of 6 CSMs, with no more than 2 CSMs worsening by at least 25% (which cannot be muscle strength). The limitations of these criteria included that equal weights had been applied to each CSM and a quantitative or continuous outcome was lacking.

Given that the TIS is focused on improvement, one of the limitations is that it cannot differentiate between no change and worsening and, therefore, these criteria might not be applicable in studies of worsening disease activity (ie, disease flare designs) in DM. However, this study will only include subjects with active disease with background immunomodulatory therapy and IgPro20 will be used as add-on therapy. It is, therefore, not expected that a relevant number of subjects will experience disease flares that meet the criteria for DOW. Any subject who meets DOW criterion will be offered standard-of-care rescue corticosteroid treatment until recovery. By definition of the primary endpoint, these rescued subjects will be classified as treatment failures (non-responders).

With the abovementioned limitations of TIS in identifying deterioration, key secondary endpoints have been defined that allow for identification of both improvement and deterioration and that are relevant in the assessment of DM. MMT-8 is a set of 8 designated muscles which will be tested bilaterally (potential score 0 to 150): 7 biaxial muscles with potential score 0 to 140 and 1 axial (neck flexors) with potential score 0 to 10. Validation of MMT-8 has demonstrated internal reliability and consistency, rater reliability, convergent construct validity, and responsiveness in assessing strength in patients with adult DM (also in PM and juvenile IIM) [Rider et al, 2010]. The MMT-8 is 1 of the CSMs and is the most heavily weighted CSM in the TIS.

The CDASI in its modified version (version 2) is a validated tool of skin disease activity (3 items) and damage (3 items) assessment. It has been developed as an instrument for clinical studies and longitudinal patient assessment [Klein et al, 2008; Goreshi et al, 2012; Yassaee et al, 2010].

These 2 validated tools (MMT-8 and CDASI) will enhance knowledge on the outcome data as key secondary endpoints, as these 2 domains (muscle strength and skin disease activity) are the most relevant manifestations of DM. They will provide evidence of treatment effect to supplement the composite improvement scale — TIS.

The primary endpoint will be assessed at Weeks 17, 21, and 25. In Study Period 2, all subjects will be on IgPro20 treatment; subjects who were previously allocated to placebo will have the opportunity to respond to IgPro20 treatment, and subjects who were already treated with IgPro20 in Study Period 1 will have the opportunity to maintain or improve their response. In addition, starting at Week 17, stable background concomitant corticosteroid treatment must be tapered, if the subject has demonstrated clinically relevant improvement, ie,  $\geq 2$  cm improvement from Baseline on a 10-cm Physician Global Disease Activity Assessment VAS (see [Section 5.3.2](#)). Tapering concomitant corticosteroid treatment will reduce the risk for steroid-related side effects, eg, uncontrolled hypertension, hyperglycemia, and weight gain.

Study Period 3 of the study will provide data on the long-term safety and efficacy of treatment with IgPro20. Eligible subjects may continue treatment with open-label IgPro20 in Study Period 3 starting at Week 53. The study will end **CCI** :

**CCI** months **CCI**

**CCI**

**CCI** for the indication Dermatomyositis, unless the decision has been made by CSLB that **CCI** **CCI** is not reasonably possible, in which case the study will end 6 months after notice is provided to the applicable regulatory authorities of that decision.

### 3.3.2 Dose Rationale

The few small studies that have utilized SCIG for treatment in patients with DM/PM relied on precedence from IVIG dosing to determine optimal SCIG dosing. From the first study in 1987 in a single subject with PM, to the Dalakas 1993 study and 2 Japanese studies, a 2 g/kg body weight per month IVIG dose was used as a standard dose in treatment of subjects with DM/PM [Dalakas, 1991; Dalakas et al, 1993; Saito et al, 2008; Miyasaka et al, 2012], and has been commonly adopted in clinical practice and standard of care. In smaller, open-label studies, similar SCIG monthly doses were used (2 g/kg body weight [Danieli et al, 2011; Gelardi et al, 2014], 1.9 g/kg body weight [Cherin et al, 2016], and 1.7 g/kg body weight [Schleinitz et al, 2008]) in subjects with DM/PM. In these studies, the standard IVIG dose for subjects with DM/PM was divided into weekly SCIG doses approximately equivalent to 0.5 g/kg body weight per week. Positive responses were noted as early as 3 months (the earliest tested time points for improvement). In addition, CSLB performed a simulation using a previously developed population PK model based on data from subjects with CIDP (mechanism of action postulated to be immunomodulatory) to assess in subjects with DM, predicted IgG exposure after treatment with a 0.5 g/kg SC dose of IgPro20. These analyses predicted that the median average concentration estimated as area under the concentration-time curve for a specific time interval ( $AUC_{0\text{-time}}$ )/dosing interval was comparable following 2 g/kg monthly IVIG (22.20 g/L) and 0.5 g/kg weekly SCIG (20.85 g/L), after 8 to 10 weeks. The analysis also predicted trough concentration ( $C_{\text{trough}}$ ) at steady state, which appears to be higher for 0.5 g/kg weekly SCIG (17.12 g/L) compared to 2 g/kg monthly IVIG (13.15 g/L). The higher  $C_{\text{trough}}$  following 0.5 g/kg SCIG dose is likely due to a shorter dosing interval following weekly dosing. Overall, this analysis provides evidence of comparable steady-state IgG exposure after SC dosing of 0.5 g/kg body weight weekly and IV dosing of 2 g/kg body weight monthly. Based on the clinical evidence and outcome of the simulations, we have chosen 0.5 g/kg body weight as the weekly IgPro20 dose in this study.

A weekly flexible SC infusion dosing regimen will be employed during the study. This means that the subject and study site can select the most appropriate and convenient regimen based on body weight and subject preference (see [Appendix 15](#) for examples). The maximum volume per infusion will be 50 mL which can be divided into up to 3 infusion sites per infusion. The infusion rate can be increased gradually to 50 mL/h per infusion site, as tolerated during the study.

This will be the first clinical study performed with IgPro20 for the treatment of DM.

### 3.4 Planned Study Duration

After up to 2 months of Screening, the duration for an individual subject is expected to be 24 weeks in Study Period 1 and 28 weeks in Study Period 2. The maximum study duration in the open-label Study Period 3 will be approximately 7 years; however, subject participation will end if the drug becomes commercially available or if there is no longer benefit from the study drug. For subjects not eligible to participate in Study Period 3, study duration will be up to 56 weeks (including the Follow-up Telephone Call).

See Section 3.7 for the definition of end of study.

### 3.5 Planned Number of Subjects

A sufficient number of subjects will be screened in order to randomize approximately 126 subjects into the study (63 per treatment sequence) at approximately 80 to 100 study sites globally. At least 10 Japanese subjects will be randomized at study sites in Japan.

### 3.6 Definition of Start of the Clinical Study

The start of the clinical study is defined as the date of the first signed informed consent of a potential subject.

### 3.7 Definition of End of the Clinical Study

The study will end CCI : [REDACTED]

CC1 months CCI [REDACTED]

CC1 [REDACTED]

CC1 [REDACTED] for the indication Dermatomyositis, unless the decision has been made by CSLB that CCI [REDACTED] is not reasonably possible, in which case the study will end 6 months after notice is provided to the applicable regulatory authorities of that decision.

### 3.8 Study Oversight

#### 3.8.1 Steering Committee

The steering committee will provide scientific support, scientific expertise for substantial amendments to the protocol, advice to the investigators on all aspects of the study, and support recruitment/feasibility of the study (ie, educational training or lectures) and preparation of publications. The steering committee will consist of external experts in the

fields of dermatology, rheumatology, neurology, and statistics who have experience treating patients with DM and/or experience in clinical studies.

### 3.8.2 Independent Data Monitoring Committee

The independent data monitoring committee (IDMC) will monitor the efficacy and safety data generated during Study Period 1 and Study Period 2 (through Week 53 / Week 56) in order to conduct assessments of the benefit-risk profile. The IDMC will consist of external experts in the fields of dermatology, rheumatology, neurology, hematology/coagulation, and statistics who have experience treating patients with DM and/or experience in clinical studies. The IDMC will receive notification of all serious adverse events (SAEs), AESIs, and deaths reported throughout the study. In addition, the IDMC will meet at regularly scheduled intervals to evaluate compiled efficacy and safety data to assess overall benefit-risk. After each meeting, recommendations will be issued to CSLB regarding the continuation of the study, potential need for protocol modifications, or study termination. No success or futility thresholds will be set for the IDMC reviews; CSLB will not stop the study based on these data unless a major safety issue has been identified (see Section 3.9). The composition, activities, and responsibilities of the IDMC will be described in the IDMC Charter.

## 3.9 Thromboembolic Event Stopping Criteria

The elevated risk of TEEs associated with IgPro20 treatment as compared with placebo will be evaluated by the IDMC on an ongoing basis and at the defined data cut points described below.

**Data Cut Point** – percentage of subjects having reached the end of the primary endpoint analysis period (Week 25):

- 25%
- 50%
- 75%
- 100%

TEE rates will be calculated for each treatment group, along with relative risk (IgPro20 over placebo) and associated 80% credibility intervals based on Bayesian technique [Barker et al, 2008] which accounts for the consideration of differential exposure times. The analysis will include data from Study Period 1 and Study Period 2, as available. Further details and calculations will be provided in the IDMC statistical analysis plan.

---

An excess of TEEs in IgPro20 over placebo will be considered if the lower limit of the 80% credibility interval for the relative risk is  $> 1.1$  (presumably an IgPro20 rate greater than 10% [relative] over placebo). In this case the IDMC may recommend stopping the study.

Further details on how the IDMC will review the TEE data and provide recommendations is included in the IDMC Charter.

Monitoring of TEE risk is described in [Section 8.1.2.2](#).

## 4 Selection and Withdrawal of Subjects

### 4.1 Eligibility Criteria

The study population will be selected on the basis of the inclusion and exclusion criteria described in the sections below. Each subject should meet all of the inclusion criteria and none of the exclusion criteria for this study. Subject eligibility should be reviewed and documented by an appropriately medically qualified member of the investigator's study team before subjects are included in the study. Full eligibility for the study will be determined at Baseline.

#### 4.1.1 Inclusion Criteria

To be enrolled and randomized into the study, subjects must meet all of the following inclusion criteria:

- 1 Capable of providing written informed consent by signing an informed consent form (ICF) and willing and able to adhere to all protocol requirements
- 2 Age  $\geq 18$  years
- 3 **Diagnosis** of at least probable IIM per EULAR/ACR Classification Criteria ([Appendix 2](#)): minimum aggregate score of 5.5 without muscle biopsy and 6.7 with muscle biopsy (historical muscle biopsy is acceptable) which includes confirmation of DM rash/skin manifestation (present or by history [historical skin biopsy is required for amyopathic DM subjects])
- 4 **Disease activity** defined by:
  - Presence of DM rash/skin manifestation (eg, Gottron's papules/sign, heliotrope rash, periorbital edema, V sign, Shawl sign) at Screening Visit - OR -

- One objective disease activity measure within 3 months before Baseline:
  - a. Magnetic resonance imaging (MRI) scan showing active inflammation (edema) of a proximal skeletal muscle - OR -
  - b. Electromyogram showing acute changes such as spontaneous activity not explained by other disease - OR -
  - c. Muscle biopsy with perivascular or perimysial inflammation - OR -
  - d. CK > 4 times the upper limit of normal ( $4 \times \text{ULN}$ )

5 **Disease severity** at Screening and Baseline defined by a minimum value of 2 cm on a 10-cm Physician Global Disease Activity VAS\* and:

- MMT-8  $\leq 142$  – OR -
- CDASI total activity score  $\geq 14$

\* On the VAS, 0 cm = absence of disease activity and 10 cm = extremely active/severe disease activity.

6 Subject has failed previous DM treatment or is on DM treatment such as immunosuppressants and/or antimalarials on a stable dose  $\geq 3$  months before Baseline; and/or oral corticosteroids ( $\leq 20$  mg/day prednisolone equivalent) on a stable dose  $\geq 1$  month before Baseline (also see [Section 7.2](#) for details)

#### 4.1.2 Exclusion Criteria

Subjects must not be enrolled or into the study or randomly assigned to treatment if they meet any of the following exclusion criteria:

- 1 Cancer-associated myositis, defined as the diagnosis of myositis within 2 years of the diagnosis of cancer
- 2 Evidence of malignancies diagnosed within the previous 5 years

*Note: Subjects with a history of carcinoma in situ of the cervix that has been excised and cured with  $\geq 5$  years since excision or subjects with documented history of treated basal or squamous cell skin cancer may be enrolled into the study.*
- 3 Physician Global Damage Assessment  $\geq 3$  on a 5-point Likert scale where a score of 3 represents severe damage
- 4 Clinically relevant improvement between Screening and Baseline, defined by  $\geq 2$  cm improvement on a 10-cm Physician Global Disease Activity Assessment VAS
- 5 Known or suspected hypersensitivity or other severe reactions to IgPro20 or to any of its excipients, or other immunoglobulins or severe reactions to blood products

6 Other significant medical conditions that could increase the risk to the subject, eg:

- History of allogeneic bone marrow/stem cell transplant/solid organ transplant
- Cardiac insufficiency (New York Heart Association Class III or IV) or unstable ischemic heart disease
- Chronic kidney disease stage IV or V
- Recent surgery requiring general anesthesia within the previous 4 weeks before Screening
- Known hyperprolinemia type I or type II
- Thrombophilic abnormalities including blood hyperviscosity, protein C or protein S deficiency, antithrombin-III deficiency, plasminogen deficiency, antiphospholipid antibodies, Factor V Leiden mutation, dysfibrinogenemia, or prothrombin G20210A mutation
- History of documented thrombotic episode, eg, pulmonary embolism (PE), deep vein thrombosis (DVT), myocardial infarction, thromboembolic stroke at any time
- More than 3 of the following specified risk factors for TEEs (documented and current conditions) occurring concurrently: atrial fibrillation, coronary disease, diabetes mellitus, dyslipidemia, hypertension, obesity (body mass index  $\geq 30 \text{ kg/m}^2$ ), recent significant trauma and immobility (wheelchair-bound or bedridden)
- Uncontrolled, severe, or rapidly progressive interstitial lung disease which will prevent the subject from successful participation in the study
- Severe skin disease at planned infusion sites that would make SC infusions infeasible
- Medical conditions whose symptoms and effects could alter protein catabolism and or IgG utilization (eg, protein-losing enteropathies, nephrotic syndrome, known immunoglobulin A [IgA] deficiency with antibodies to IgA)

7 Other conditions which would prevent correct assessment or lead to impaired muscle strength (eg, other neurological disorders including, but not limited to, Parkinson's disease or severe musculoskeletal conditions like severe osteoarthritis or deformities)

8 Laboratory exclusions at screening:

- Positive result at for any of the following: human immunodeficiency virus (HIV), hepatitis B virus (HBV), or hepatitis C virus (HCV)
- Creatinine  $> 1.5 \times$  ULN or blood urea nitrogen (BUN)  $> 3 \times$  ULN

9 Any of the following therapies:

- Within **1 month** before Baseline: IM, IV, or intra-articular corticosteroids including adrenocorticotropic hormone (any dose), doses  $> 20$  mg/day prednisolone equivalent (any route), or any change to physiotherapy
- Within **2 months** before Baseline: IgG (Note: Subject may enroll  $< 2$  months after stopping IgG therapy if clinical deterioration is experienced after withdrawal.)
- Within **3 months** before Baseline: plasma exchange or plasmapheresis
- Within **6 months** before Baseline: cyclophosphamide or alkylating agents
- Within **6 months or 5 half-lives** of the drug, whichever is longer, before Baseline: other biologic therapies including investigational agents
- Within **9 months** before Baseline: rituximab or evidence of persistent B cell depletion after stopping therapy

10 Male subject or female subject of childbearing potential either not using or not willing to use a medically reliable method of contraception (see [Section 7.4.2](#)), not sexually abstinent during the study, or not surgically sterile before study enrollment

11 Pregnant or breastfeeding

12 Alcohol, drug, or medication abuse within 1 year of providing informed consent

13 Previously received IMP in this study or failed Screening more than 1 time in this study

14 Involved in the planning and/or conduct of this study (applies to CSLB staff, staff at the study site, and third-party vendors)

15 Any issue that, in the opinion of the investigator, would render the subject unsuitable for participation in the study or unable to comply with study procedures, eg, inability to self-administer IMP or by aid through a caregiver

### 4.1.3 Eligibility Criteria for Study Period 3

At the Week 53 Visit, subjects may continue to Study Period 3 if they have a TIS  $\geq$  20 points at the Week 49 Visit. Subjects who participate in Study Period 3 will continue to receive open-label IgPro20 0.5 g/kg SC infusions weekly until the end of the study ([Section 3.7](#)).

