At Week 53, eligibility for continuation of open-label IgPro20 treatment in Study Period 3 will be confirmed based on the TIS conducted in Week 49 (see [Section 4.1.3](#) for details). If subjects do not continue treatment after Week 53, an EOP2 Safety Follow-up Telephone Call will be conducted to assess the subject's safety status at Week 56 (or 4 weeks after the final infusion). If the subject continues treatment in Study Period 3, the telephone call will not be performed.

See [Section 3.7](#) for the definition of study end.

Figure 1

Study Design

Abbreviations: DM = dermatomyositis; DOW = Definition of Worsening; EOP = End of Study Period; TIS = Total Improvement Score.

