## 4.3 Discontinuation of IMP and Subject Study Withdrawal

### 4.3.1 Discontinuation of IMP

If any of the following apply, the subject must discontinue IMP:

- Subject wishes to discontinue IMP
- Subject withdraws consent for study participation
- Investigator advises that the subject's safety or well-being could be compromised by further treatment
- Subject or caregiver is not able to administer the SC infusions at home by Week 4
- Subject has confirmed diagnosis of DVT or PE
- Subject has Grade 3 hemolysis (see [Section 8.1.2.3](#))
- Subject becomes pregnant
- Relevant treatment noncompliance

During participation in Study Period 3, if the investigator determines that the subject is no longer benefiting from IgPro20 and/or is showing signs of clinical deterioration in DM status, the subject must be discontinued from the study.

The investigator should record in the electronic case report form (eCRF) and in the subject's medical records the reason and date of IMP discontinuation.

Subjects who discontinue IMP will be encouraged to remain in the study until Week 25 if discontinuation occurs during Study Period 1, or until Week 53 if discontinuation occurs during Study Period 2, in order to collect study assessments. The Safety Follow-up Telephone Call will not be performed for subjects who discontinue IMP treatment but remain in the study for at least 1 subsequent study visit 4 weeks after IMP discontinuation. See [Schedule of Assessments](#) for details on assessments no longer collected after IMP discontinuation if the subject remains in the study, and Section 4.3.2 for details on handling subject withdrawal from study.

Subjects who discontinue IMP during Study Period 3 will be withdrawn from the study. Withdrawal from IMP Study Period 1 or Study Period 2 renders a subject ineligible for participation in Study Period 3 of this study.

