#### **4.3.5 Consequences of Subject Withdrawal or IMP Discontinuation**

Subjects who have been withdrawn from the study or who have discontinued IMP before Week 25 will be considered non-responders for the primary endpoint analysis, except if withdrawal or discontinuation was due to the Ukraine war (see [Section 10.4.2](#)) Withdrawal from IMP during Study Period 1 or Study Period 2 renders a subject ineligible for participation in Study Period 3 of this study.

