### 8.1.2.2 Monitoring for Thromboembolic Events (TEEs)

To reduce the risk of potential TEEs, this study excludes specific patient groups ([Section 4.1.2](#), exclusion criterion 6 items pertaining to TEE risk). Nevertheless, TEE risk will be continuously monitored during the study.

---

The Treating Physician will assess the subject for the suspicion of a TEE per standard of care at every study visit during all Study Periods.

If there is suspicion of DVT or PE during Study Periods 1 or 2, the Wells' Criteria for DVT ([Table 9](#)) or Wells' Criteria for PE ([Table 10](#)) will be assessed and entered in the eCRF [[Modi et al, 2016](#); [Wells' Criteria for DVT](#); [Doherty, 2017](#); [Wells' Criteria for Pulmonary Embolism](#)].

A score of  $> 1$  on the Wells' Criteria for DVT requires diagnostic imaging (lower extremity ultrasound) to rule out DVT. A score of  $> 1$  on the Wells' Criteria for PE requires additional imaging, (eg, computerized tomography scan, ventilation/perfusion scan, pulmonary angiography, or other modalities) be performed as per the site's standard of care.

When a diagnosis of DVT or PE is confirmed, IMP treatment must be discontinued; however, the subject may continue in the study for other study assessments up until Week 53. During Study Period 3, there will be no formal assessment of Wells' Criteria. TEEs will be monitored as part of standard assessment for AEs at each monthly site visit. If a TEE occurs during participation in Study Period 3, the subject must be discontinued from the study.

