- IMP assignment
- Vital signs

- Safety assessments
- Collection of urine sample for hCG pregnancy test, if applicable
- Collection of blood samples for exploratory biomarkers (serum analysis)
- Collection of blood samples to assess the following:
  - Muscle enzymes
  - Coagulation
  - Serum IgG
- Subject SC Infusion Diary review
- Document AEs
- Document concomitant therapies
- Document any change to physiotherapy since the previous study visit
- Assess if subject has clinically relevant improvement, and if so, initiate oral corticosteroid taper
- Individual CSMs
- CDASI

#### 8.5.4.7 Week 53

Eligibility for continuation of treatment in Study Period 3 is based on a TIS of  $\geq 20$  points at Week 49 and is to be confirmed at the Week 53 Visit. If the subject is not eligible to continue treatment with IgPro20, study participation will end with the Week 56 Safety Follow-up Telephone Call (see [Section 8.5.4.8](#)). If a subject is withdrawn from the study before the Week 53 Visit, the investigator should make every effort to perform the assessments scheduled for the Week 53 Visit:

- General physical examination
- 12-lead ECG
- Body weight
- Waist circumference
- IMP assignment, if subject is eligible to continue treatment with IgPro20 in Study Period 3

- Vital signs
- Safety assessments
- Collection of urine sample for hCG pregnancy test, if applicable
- Collection of blood samples for virology retention and exploratory biomarkers (RNA and serum analyses)
- Collection of blood samples to assess the following:
  - Hematology
  - HbA1c
  - Muscle enzymes
  - Other biochemistry
  - Coagulation
  - Serum IgG
  - ANA, MSA, and MAA
- Subject SC Infusion Diary review
- Document AEs
- Document concomitant therapies
- Document any change to physiotherapy since the previous study visit
- DOW (only applicable to subjects who discontinue IMP treatment before Week 25)
- Individual CSMs
- CDASI
- 5-D Itch Score
- Timed Up and Go
- EQ-5D-5L, WPAI-GH, TSQM-9

- Document reason for withdrawal, if applicable
- Assess the subject's eligibility for treatment continuation in Study Period 3, if applicable

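### Entry to Study Period 3 has no thromboembolic-event criterion, so a subject kept on IMP after a non-DVT/PE event in Periods 1-2 may start long-term open-label dosing

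*Protocol*

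**What the plan says.** **Entry to Period 3.** Protocol 4.1.3 states: "At the Week 53 Visit, subjects may continue to Study Period 3 if they have a TIS" of 20 or more at Week 49. Section 8.5.4.7 says the same: "Eligibility for continuation of treatment in Study Period 3 is based on a TIS of" 20 or more at that visit. Section 3.1 adds that "eligibility for continuation of open-label IgPro20 treatment in Study Period 3 will be confirmed based on the TIS conducted in Week 49". Section 3.2 is firmer: subjects who show benefit "at Week 49 will receive open-label 0.5 g/kg IgPro20 until the end of the study". The synopsis and glossary carry the same test.

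**The other bar.** Section 4.3.5 says: "Withdrawal from IMP during Study Period 1 or Study Period 2 renders a subject ineligible" for Period 3, and 4.3.1 agrees.

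**Stopping IMP in Periods 1-2.** Sections 4.3.1 and 8.1.2.2 require IMP to stop for a confirmed DVT or PE. No other thromboembolic diagnosis is named. The list of mandatory stops in 4.3.1 also includes a general safety clause: "Investigator advises that the subject's safety or well-being could be compromised by further treatment".

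**TEEs at enrolment and in Period 3.** Exclusion criterion 6 in 4.1.2 lists: "History of documented thrombotic episode, eg, pulmonary embolism (PE), deep vein thrombosis (DVT), myocardial infarction, thromboembolic stroke at any time". Section 8.1.2.2 says: "If a TEE occurs during participation in Study Period 3, the subject must be discontinued from the study". Section 9.1.3 defines TEEs by three MedDRA queries, one of them arterial, so the term is wider than DVT and PE.

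**The concern.** The sponsor treats a thrombotic event as incompatible with treatment at two points, before enrolment and during Period 3, and at both the rule covers arterial as well as venous events. At the point between them, the Week 53 decision to start open-label treatment, the written criterion concerns efficacy only.

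Only patient safety is at stake. The decision opens the longest exposure in the study, with less structured oversight than before: no formal Wells' scoring (Protocol 8.1.2.2), no D-dimer in the Period 3 schedule (Protocol Table 3), and no IDMC review of Period 3 data (SAP 4.6.3). A subject with a recent infarction or stroke could cross into that period without the protocol naming the event as a reason to refuse.

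**Working it through.** The plan states no figure on this point, so the check is a trace of the rules, followed by a simple exposure count.

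**Step 1. Look for a TEE condition on entry.** The Period 3 entry test is stated seven times in the protocol: synopsis, glossary, 3.1 (twice), 3.2, 4.1.3 and 8.5.4.7. Statements that add a TEE condition: 0 of 7. Section 4.1 fixes full eligibility at Baseline, and no repeat check of the 4.1.2 exclusions is stated for Week 53.

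**Step 2. Set the rules side by side.**

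| Point in the study | Confirmed DVT or PE | Other TEE (eg, infarction, thromboembolic stroke) |
|---|---|---|
| Enrolment (4.1.2, criterion 6) | Barred if in history | Barred if in history |
| Periods 1-2 (4.3.1, 8.1.2.2) | IMP must stop | No event-specific rule; general safety clause applies |
| Entry at Week 53 (4.1.3, 8.5.4.7, 4.3.5) | Barred through IMP withdrawal | Not barred if IMP continued and Week 49 TIS is at least 20 |
| During Period 3 (8.1.2.2) | Must leave the study | Must leave the study |

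One cell is out of line with its neighbours: entry at Week 53 after a non-DVT/PE event.

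**Step 3. Follow one case.** A subject has an infarction at Week 52, the investigator keeps the subject on IMP, and the Week 49 TIS was 20 or more. No protocol rule bars entry. The same event at Week 54, after entry, means mandatory exit.

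**Step 4. Size the exposure that entry opens.**
- Weekly doses in Periods 1-2: 24 + 28 = 52.
- Ceiling for Period 3, from the maximum of about 7 years in 3.4: 7 × 52 = 364.
- Ratio: 364 / 52 = 7.

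This ratio is an upper limit on exposure and not a measure of risk, because participation ends earlier on commercial availability or loss of benefit. No event rate is assumed, and the documents give none.

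**The case against.** The strongest answer is that the safety clause in 4.3.1 is itself a mandatory stop with a low threshold. The gap opens only if an investigator who knows of an infarction or stroke judges that further dosing could not compromise safety. Around that judgement stand other safeguards:
- The investigator or sponsor may withdraw a subject (4.3.2).
- TEEs are reported on the expedited timetable (9.6.2), and the IDMC is notified of them throughout the study (3.8.2).
- The Treating Physician assesses for TEE at every visit in all periods (8.1.2.2).
- The Week 53 visit includes a physical examination, ECG, D-dimer and TEE monitoring.

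All of this stands, and it makes the case uncommon. But none of it sets an entry criterion, and the sponsor did not leave the same question to judgement at enrolment or during Period 3. The permissive wording of 4.1.3 helps little, because 3.2 is worded as an entitlement.

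A second answer is that a bar creates its own asymmetry. A subject with an infarction at Week 5 could receive 52 − 5 = 47 further weekly doses by judgement and then be refused at Week 53. A Sequence B subject whose event occurred on placebo would also be refused. That is a real cost. It is acceptable because Week 53 is a separate decision to begin a much longer exposure, and the criterion is no broader than the rule already in force within Period 3.

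Third, the enrolment exclusion and the Period 3 rule do not strictly address a prior event that has been reported and reviewed. This is correct: they show the sponsor's own standard and do not formally contradict 4.1.3. The IDMC Charter and Investigator's Brochure were not available and might say more.

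**Conclusion.** The point holds as a minor, patient-safety-only improvement. It rests on the protocol text as written and on the assumption that neither the IDMC Charter nor the Investigator's Brochure supplies an entry rule.

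A reader might infer three stronger things that the documents do not support:
- **That investigator discretion after a non-DVT/PE event in Periods 1-2 is itself a flaw.** Section 4.3.1 handles such events by case judgement under a mandatory safety clause, and nothing here shows that to be wrong.
- **That TEE surveillance lapses in Period 3.** Formal Wells' scoring and IDMC data review end, but assessment at every visit, monthly adverse event monitoring and IDMC notification continue.
- **That trial results are affected.** The primary endpoint is settled at Week 25, the TEE relative-risk rule uses Periods 1 and 2 (Protocol 3.9, SAP 11.3), and Period 3 analyses are descriptive (Protocol 10.5).

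**What to change.** In 4.1.3 and 8.5.4.7, after the Week 49 TIS condition, add: *and no TEE (AESI as defined in Section 9.1.3, diagnosis documented by the investigator) during Study Period 1 or 2*. The reference to a documented diagnosis is needed because 9.1.3 lists MedDRA queries but sets no standard for confirming an event. The synopsis, glossary, 3.1 and 3.2 can point to 4.1.3.

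The cost is one phrase in two sections plus cross-references, in a single protocol amendment. No new visit, test or staff is needed. The downside should be stated openly in the amendment: a benefiting subject with such an event, including one that occurred on placebo, loses access to Period 3. Management of these events within Periods 1-2 stays as it is.

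Optionally, repeat the Period 3 TEE exit rule from 8.1.2.2 in the Period 3 paragraph of 4.3.1, which now names only loss of benefit and clinical deterioration. That is a consistency edit, and the fix does not depend on it.
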